#### **PASE**

The PASE measures the level of physical activity in individuals age 65 and older. The PASE is comprised of measures of self-reported occupational, household, and leisure activities during a one-week period. The PASE consists of 12 items which determine the frequency and duration of leisure activities (e.g., sports, jogging, swimming, strengthening and endurance exercise), household activities, and work-related activities. Items are scored differently depending upon the type of activity that is being quantified. Participation in leisure-time and strengthening activities are scored as never, seldom (1-2 days per week), sometimes (3-4 days per week), and often (5-7 days per week). Duration of these activities is scored as less than 1 hour, 1-2 hours, 2-4 hours and more than 4 hours. Household and work related activities are scored as yes or no. In work related activities, paid or unpaid work is scored in total hours per week. The total PASE score is computed by multiplying either the time spent in each activity (hours per week) or participation (i.e., yes/no) in an activity, by empirically derived item weights and then summing overall activities. The overall PASE score ranges from 0 to 400 or more, where higher scores indicate greater levels of physical activity.

#### **SEPA**

The SEPA questionnaire assesses how confident individuals are in their ability to be physically active in a variety of situations, including when they are: tired, in a bad mood, do not feel they have enough time, on vacation, when it is snowing or raining. The SEPA consists of 5 items and each item is presented in a 5 point Likert-type format. Each item uses the following descriptors for each item: not at all confident, slightly confident, moderately confident, very confident, and extremely confident. These correspond to an ordinal scale of 1-5. The point value from each question is summed for a total score. Higher scores indicated higher levels of confidence in the ability to be physically active.

#### **SF-12**

The SF-12 is used to assess functional health and well-being from the patient's point of view. The SF-12 consists of 12 items which assess all 8 domains of health, including: physical functioning, role-physical, bodily pain, general health, vitality, social functioning role-emotional and mental health. Each item is presented in either a 3 or 5 point Likert-type format. Pre-coded values are assigned to each possible answer for each item. Raw scores from each item are totaled, and raw scores can be transformed into 0-100 scale scores. Higher scores on the SF-12 indicate better general health perceptions.

#### **Charlson Comorbidity Index**

The Charlson Comorbidity Index is a method of categorizing comorbidities of patients based on the International Classification of Diseases (ICD) diagnosis codes found in administrative data. Each comorbidity category has an associated weight, based on the adjusted risk of mortality or resource use, and the sum of all

the weights results in a single comorbidity score for a patient. A score of zero indicates that no comorbidities were found. The higher the score, the more likely the predicted outcome will result in mortality or higher resource use.

### **VAS to determine tolerability of walking, current level of knee pain, and likelihood to continue current level of physical activity**

The VAS for tolerability of walking will be completed immediately upon completion of the first trial of the 20-meter walk test. Participants are asked to make a vertical line on a 100mm solid line to indicate how tolerable they feel walking was during the task just completed. The VAS ranges from “Not at all Tolerable” on the left to “Extremely Tolerable” on the right. VAS scores closer to 100, or marks closer to the rightward end, indicate a greater tolerability of walking. The VAS for the current level of knee pain asks participants to make a vertical line on a 100mm solid line to indicate how much pain they currently have in their knee. The VAS ranges from “No Pain” on the left to “Worst Pain Imaginable” on the right. VAS scores closer to 100, or marks closer to the rightward end, indicate a greater amount of knee pain. The VAS for the likelihood to continue their current level of physical activity asks participants to make a vertical line on a 100mm solid line to indicate how likely they are to continue their current level of physical activity. The VAS ranges from “Not at all Likely” on the left to “Extremely Likely” on the right. VAS scores closer to 100, or marks closer to the rightward end, indicate a greater likelihood of continuing the current level of physical activity.

### *8-Week Follow Up Assessment*

Six questionnaires will be completed during the baseline assessment, which occurs within 7 days prior to the initiation of the intervention and includes 1) the Physical Activity Scale for the Elderly (PASE), 2) Self-Efficacy for Physical Activity (SEPA), 3) the Short Form 12 (SF-12), 4) the Charlson Morbidity Index, 5) Visual Analog Scales (VAS) to determine the likelihood to continue current level of physical activity, current level of knee pain, and tolerability of walking, and 6) Knowledge of Group Assignment for Study Participants. One questionnaire will be completed by the member of the research team who will be conducting the 8-week follow-up which is the Knowledge of Group Assignment for Study Investigators.

### **PASE**

The PASE measures the level of physical activity in individuals age 65 and older. The PASE is comprised of measures of self-reported occupational, household, and leisure activities during a one-week period. The PASE consists of 12 items which determine the frequency and duration of leisure activities (e.g., sports, jogging, swimming, strengthening and endurance exercise), household activities, and work-related activities. Items are scored differently depending upon the type of activity that is being quantified. Participation in leisure-time and strengthening activities are scored as never, seldom (1-2 days per week), sometimes (3-4 days per week), and often (5-7 days per week). Duration of these activities is scored as less than 1 hour, 1-2 hours, 2-4 hours and more than 4 hours. Household and work related activities are scored as yes or no. In work related activities, paid or unpaid work is scored in total hours per week. The total PASE score is computed by multiplying either the time spent in each activity (hours per week) or participation (i.e., yes/no) in an activity, by empirically derived item weights and then summing overall activities. The overall PASE score ranges from 0 to 400 or more, where higher scores indicate greater levels of physical activity.

### **SEPA**

The SEPA questionnaire assesses how confident individuals are in their ability to be physically active in a variety of situations, including when they are: tired, in a bad mood, do not feel they have enough time, on vacation, when it is snowing or raining. The SEPA consists of 5 items and each item is presented in a 5 point Likert-type format. Each item uses the following descriptors for each item: not at all confident, slightly confident, moderately confident, very confident, and extremely confident. These correspond to an ordinal scale of 1-5. The point value from each question is summed for a total score. Higher scores indicated higher levels of confidence in the ability to be physically active.

### **SF-12**

The SF-12 is used to assess functional health and well-being from the patient's point of view. The SF-12 consists of 12 items which assess all 8 domains of health, including: physical functioning, role-physical, bodily pain, general health, vitality, social functioning role-emotional and mental health. Each item is presented in either a 3 or 5 point Likert-type format. Pre-coded values are assigned to each possible answer for each item. Raw scores from each item are totaled, and raw scores can be transformed into 0-100 scale scores. Higher scores on the SF-12 indicate better general health perceptions.

### **Charlson Comorbidity Index**

The Charlson Comorbidity Index is a method of categorizing comorbidities of patients based on the International Classification of Diseases (ICD) diagnosis codes found in administrative data. Each comorbidity category has an associated weight, based on the adjusted risk of mortality or resource use, and the sum of all the weights results in a single comorbidity score for a patient. A score of zero indicates that no comorbidities were found. The higher the score, the more likely the predicted outcome will result in mortality or higher resource use.

### **VAS to determine tolerability of walking, current level of knee pain, and likelihood to continue current level of physical activity**

The VAS for tolerability of walking will be completed immediately upon completion of the first trial of the 20-meter walk test. Participants are asked to make a vertical line on a 100mm solid line to indicate how tolerable they feel walking was during the task just completed. The VAS ranges from "Not at all Tolerable" on the left to "Extremely Tolerable" on the right. VAS scores closer to 100, or marks closer to the rightward end, indicate a greater tolerability of walking. The VAS for the current level of knee pain asks participants to make a vertical line on a 100mm solid line to indicate how much pain they currently have in their knee. The VAS ranges from "No Pain" on the left to "Worst Pain Imaginable" on the right. VAS scores closer to 100, or marks closer to the rightward end, indicate a greater amount of knee pain. The VAS for the likelihood to continue their current level of physical activity asks participants to make a vertical line on a 100mm solid line to indicate how likely they are to continue their current level of physical activity. The VAS ranges from "Not at all Likely" on the left to "Extremely Likely" on the right. VAS scores closer to 100, or marks closer to the rightward end, indicate a greater likelihood of continuing the current level of physical activity.

### **Knowledge of Group Assignment – Study Participant**

Participants are asked to indicate which of the interventions groups they feel they were assigned to during the intervention. Data from this questionnaire will determine if participant blinding was achieved.

### **Knowledge of Group Assignment – Study Investigator**

Study investigators are asked to indicate which of the interventions groups they feel the participant they collected the 8-week follow up assessment on was assigned to during the intervention. Data from this questionnaire will determine if investigator blinding was achieved.

## **3.n.2 General Instructions for Completing Forms**

### *Instructions for Study Participants*

All questionnaires are to be completed by study participants in black ink. Individual instructions for completing each questionnaire are clearly written on the top of the first page of the questionnaire. Participants will be read the instructions by either the Principal Investigator, Study Coordinator, or Research Assistant. Study participants are instructed to only write in the spaces provided, to not skip any questions, and to not use abbreviations. If an error has been made on any study form, a single line will be placed through the erroneous entry. The date of the error will be recorded and the participant initial next to the error. The participant will be asked to indicate the correct response in the event an error is made.

### *Instructions for Study Investigators*

Study investigators will complete the header of each questionnaire prior to completion. The study participants ID will be written on each page of every questionnaire. The date of completion will be written in a Month/Day/Year format, and time of completion will be written using a 24 hour clock. If an error has been made on any study form, a single line will be placed through the erroneous entry. The date of the error will be recorded and the investigator initials next to the error. The investigator must indicate the correct response in the event an error is made.

### *Minimizing Incomplete Forms*

In order to minimize incomplete study forms, the Principal Investigator, Study Coordinator or Research Assistant will review each study form the participant completes. In the event a participant has failed to complete a question, the participant will be asked to complete the question that was not completed. If data is not available for an item, the item is to be circled and the reason the data is not completed is to be written next to the item. If an evaluation was not done, ND will be written next to the incomplete item with the reason the evaluation was not done or the item was not completed. If the information is not available, but the evaluation or form was completed, then NAV is to be written on the study form. In the event NAV is written on a study form, the Principal Investigator, Study Coordinator or Research Assistant will contact the participant in order to attempt to obtain all information and ensure all study forms are complete.

Following completion of the self-reported study forms the Principal Investigator, Study Coordinator or Research Assistant will review each study form the participant completes in order to ensure all items are completed properly and each answer is legible. If the answer to an item is not legible, the member of the study team will ask the study participant to clarify their answer and ensure it is legible.

### *Guidelines for Incomplete and Illegible Forms*

If an item on a study form is incomplete or illegible the item will be circled on the study form by the Principal Investigator, Study Coordinator or the Research Assistant. The reason for incomplete or illegible will be written on the top of the first page of the study form if the entire document is incomplete or illegible. If only certain items are incomplete or illegible the reason will be written next to the circled item. If an entire page of a study form cannot be completed a diagonal line will be drawn through the form. The Principal Investigator, Study Coordinator or Research Assistant will then write NOT DONE, NOT AVAILABLE, or NOT APPLICABLE on the page as appropriate. Regardless of whether or not a form is incomplete or illegible the header information will be completed on each and every page of the study forms.

### **3.n.3 Retention of Study Documents**

All study related files will be maintained for **at least 7 years**, as mandated by the Institutional Review Board at the University of North Carolina at Chapel Hill. All study files will remain in a locked file cabinet located within the Neuromuscular Research Laboratory, which is secured via swipe card access. Once 7 years' time has passed, all study documents will be shredded.

### **3.n.4 Administrative Forms**

Five administrative forms have been included in order to assist with the management of participant enrollment. Each administrative form is described below and is included.

### **Telephone Contact Log**

The telephone contact log will be used to document all conversations regarding the study and study participants. The contact log will be used any time the Principal Investigator, Study Coordinator or Research Assistant makes a telephone call to either a member of the research team or a study participant in regards to

this study. The Principal Investigator, Study Coordinator or Research Assistant will record the date of the phone call, their name, the individual the call is made to, the reason for the call and the length of the conversation.

### **Screening Log**

The screening log will be used to record all participants which are screened for participation into the study. The screening log will be kept up to date at all times throughout the study.

### **Participant Identification Code List**

The participant identification code list will be used to document the participant's name, medical record number, randomization number, and study entry and study exit dates. The participant identification code list will be kept within a located filing cabinet located in the Principal Investigators office, which is a secure location and separate from all other study files.

### **Signature Log**

The signature log will contain the signature of all member of the study team. The Principal Investigator and Study Coordinator will be responsible for designating members of the research team who are approved to make form entries and changes. In the event a member of the research team is removed from the team for any reason, the Principal Investigator will record the date the member of the research team is removed.

### **Site Visit Log**

The Principal Investigator, Study Coordinator and Research Assistant will each visit the Meadowmont Physical Therapy Clinic in order to complete initiation and training, as well as to meet with study participants each week of the intervention in order to collect all study forms. The name of the research team member and the date, time and reason for the visit to the physical therapy clinic will be recorded each time a visit is made.

## **3.m Study Compliance**

### **Definitions**

Protocol deviation - any change, divergence, or departure from the study design or procedures of a research protocol that is under the investigator's control and that has not been approved by the IRB.

Protocol violation - a deviation from the IRB-approved protocol that may affect the subject's rights, safety, or wellbeing and/or the completeness, accuracy and reliability of the study data.

### **Procedures**

In order to minimize the risk of a protocol deviation or protocol violation [name], a licensed physical therapist, will track compliance of the study procedures related to informed consent, randomization, follow up testing, IRB compliance, and compliance to treatment protocols.

*Randomization* – [name] will confirm that the first 10 patients that are found to be eligible for the study meet all inclusion and exclusion criteria prior to randomization. For patients 10-90, [name] will monitor patient recruitment by checking the patient files for all patients that were randomized to a group on a monthly basis (approximately 5 at a time). Potential violations will include: informed consent not obtained or a patient is randomized that does not fit inclusion/ exclusion criteria). [name] will confirm that the first 5 participants are randomized to the correct group by cross referencing randomization lists, which will ensure that assignments in randomization envelopes correspond with the master randomization lists. Randomization will be crossed referenced by a randomly selected patient each month.

*Follow-Up Testing* – Each month [name] will ensure that follow-up testing of each patient was performed in

*IRB Compliance* - [name] will confirm each month that protocol information and consent forms used are approved by the IRB and any changes in the protocol are confirmed with the IRB and have been included in the revised protocol and regulatory documentation.

*Compliance of Treatment Protocols* – [name] will use visit the Meadowmont Physical Therapy Clinic on a monthly basis and observe the administration of the therapeutic exercises that are detailed in section 3.g. [name] will determine and document if the Physical Therapists are complaining with the descriptions of the exercises and dictating treatment progressions correctly.

All reports will be provided to [name], the principal investigator 72 hours after the evaluation and any protocol deviations or violations will be dealt with accordingly. Biweekly meetings are scheduled with the study team to assist in a rapid implementation for any issues brought up in [name] reports, yet the PI may take immediate action with the study team to ensure adherence of study protocols if an urgent issue is brought to attention. The PI will report protocol violations and deviations to the IRB at the University of North Carolina at Chapel Hill within 48 hours of the violation/deviation via the online IRBIS reporting system. Protocol deviations will be addressed by modification to the IRB protocol, informed consent form and manual of operating procedures if necessary. All events will be reported at the time of the biannual at submission of the safety report. The study coordinator, [name], will maintain a log of all protocol deviations/violations and should report them to [name] each month.

In the case of serious violations a review of the personnel involved will be performed by [name] and [name]. Depending on the nature of the violation or deviation, study recruitment and treatment may be stopped until the violation/ deviations is addressed. Actions may be taken to remove a patient from the data set if the deviation affects the data collected. It is possible that if a violation is deemed egregious study personnel may be dismissed from further involvement in the study in order to ensure future validity of the data collected and safety for study participants.

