### **3.g Study Intervention**

#### *Intervention Overview*

The current study is a **Phase 1 clinical trial** that will have three randomized groups. All groups will receive the same supervised, standardized TE program at the UNC Meadowmont Physical Therapy Clinic. *TENS+TE* and *sham TENS+TE* patients will be instructed to utilize their device during all 12 physical therapy sessions as well as 8 hours per day when they are the most active for 4-weeks (28 days). Twelve TE sessions over 4 weeks is the current standard of care for patients with knee OA at the UNC Meadowmont Physical Therapy Clinic. Additionally, previous data indicate strong effect sizes for neuromuscular improvements following a 12 session/4-week intervention. Patients included in this study will be treated by 1 of 4 physical therapists (PT) associated with this study during each session (see participating physical therapists listed below). Patients in all groups will receive TE for their involved leg 3 times per week for 4 weeks (12 sessions). The PTs will review each patient's medical history and physician instructions before starting TE. A PT will conduct a lower extremity physical assessment prior to beginning rehabilitation and following the 4-week intervention for clinical use. *The overall goals of the TE program are to increase lower extremity strength and function.* Progressive exercise will be similar to that previously reported by the PI. Procedural reliability of the intervention will be maximized using: 1) training sessions for the PTs to ensure all exercises are taught and progressed in the same manner, 2) tracking compliance of *TENS/ sham TENS+TE*, 3) biweekly review patient charts regarding exercises, and 4) biweekly evaluation of therapeutic exercise delivery on a subset of patients at random time points using a rubric. Lower extremity strengthening will be progressed through open and closed chain strengthening (see exercises in tables X-X). Range of motion limitations and soreness will be addressed or managed with stretching, manual therapy, and/or cryotherapy. All strengthening exercises will be systematically progressed, on an individual basis, using the daily adjustable progressive resistive exercise system. Functional exercises will be progressed according to the patients' ability and any reactive inflammation from TE.

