**The Experimental TENS Group (*TENS+TE*):** Patients assigned to the TENS+TE group will receive a *Select System TENS unit (EMPI, Inc., St. Paul, MN)*, self-adhesive electrodes and batteries upon admission into the clinical trial and allocation into the TENS +TE group. TENS+TE patients will meet with a member of the study team in a private room at the Proaxis clinic prior to the initial visit with the PT. Patients will be taught how to apply the electrodes on the knee joint and educated on how to operate the TENS unit. An instruction manual will be provided to the patients for reference purposes explaining device operation and a reminder for how to escalate dosing parameters; these dosing parameters were successfully used in our pilot study. Patients will be provided with the phone number of an unblinded member of study team to call with questions. The primary method of collecting TENS compliance will be using a digital memory chip built into the TENS units that records the length of time each participant uses the device. Patients will log the hours of daily use as a backup.

**The Sham Group (*sham TENS+TE*):** Sham TENS+TE patients will receive a *Select System TENS unit (EMPI, Inc., St. Paul, MN)* specifically configured to cease TENS current output 20 seconds after the participants initiation. For blinding purposes, patients will be told that they should feel a brief stimulation (~20 seconds) that will become “sub-sensory” in nature. In reality, the Sham TENS unit will emit no current after 20 seconds. The sham TENS unit will have a functioning display identical to the active TENS units indicating the sham output voltage. The instruction manual that the sham group receives will not have any dose escalating procedures.

**The Comparison Group (*TE only*):** The role of the comparison group is to provide data on how traditional TE affects the outcome measures. The TE only group will allow us to assess how the addition of TENS and sham TENS to traditional TE will augment the effects of traditional TE. The TE only group will receive exactly the same TE as the TENS+TE and the sham TENS+TE in order to specifically determine what changes are attributed to TE only and not the neuromuscular changes brought about by *TENS+TE* or *sham TENS+TE*.

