### 3.g.1 Randomization

Individuals who screen into the study and complete baseline testing will be randomized to one of 3 groups. Participants will be randomized into an intervention group before meeting the patient at the clinic but following a confirmation phone call. The confirmation phone call will occur 72- 24 hours prior to the first physical therapy appointment. The purpose of the confirmation phone call is to minimize the risk that patients drop out of the study prior to being randomized to a group. After screening, patients will be stratified to one of four strata based on CAR (low < 80%, High  $\geq$  80%; Low Kellgren-Lawrence 2, High Kellgren-Lawrence 3 and 4). A separate blocked randomized list (block of 6) will be created by [name] for each strata. A set of opaque sealed envelopes will contain the randomized group assignment for each participant. [name] will have the randomized lists in case cross-referencing is ever needed in the future. The principal investigator will check with [name] for each of the first 10 participants that are randomized from each list match the assignment from the envelopes, and at every 5th randomized participant for the rest of the study. During assembly of the envelopes a 5th strata list will be developed and cross referenced immediately after assembly as a quality control measure.

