### 3.h Blinding and Unblinding

The current study is a double-blinded randomized controlled trial, where the investigators evaluating study outcomes as well as patients in the TENS+TE and Sham TENS + TE groups will be blinded. There will be no effort to blind patients in the control or TE only group.

The unblinded personnel in the study will be [name] (in charge of back-up randomizations lists), [name] (in charge of screening, randomization and scheduling), [name] (in charge of screening, randomization and scheduling), and [name] (in charge of initial randomization and study analysis). All efforts will be made to maintain the blinding of all other study personnel collecting data as well as the patients in the study. We will assess blinding of patients and study personnel at the end of the study to determine efficacy of the blinding procedures. We will not unblind any of the blinded personnel until after the study has been completed and all outcome measures for all patients have been analyzed and imputed into databases.

We will unblind the patients if: 1) they sustain a medical condition that requires that they know their group assignment or 2) they request the information in writing following the completion of the project in that all outcome measures for all patients have been analyzed and imputed into databases.

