### **3.O Data Management**

Epi Info, which is a product of the Centers of Disease Control, will be used to enter outcomes data and export data to SPSS which will be used for data analysis.

**Data tracking** – The status of enrollment will be tracked with Epi Info. A separate telephone call log will be kept with the number of people that contact the study team who are interested in the study. We will also keep a log of encounters the study team may have with patients at the clinic. We will keep data indicating how many patients screen out of the study over the telephone or in the clinic due to exclusion criteria or disinteresting

participating. We will collect the number of patients that complete the initial consenting process and screen into the study following the screening visit to the laboratory. Finally we will determine how many people that screen into the study are randomized into a treatment condition.

**Data Entry** – Data will be entered from electronic files or paper surveys. Outcome measures will be cut and pasted from excel or collection software into Epi Info to minimize data entry error. Two separate investigators will calculate paper questionnaire scores with a Microsoft Excel spreadsheet to minimize mathematical error prior to entry. All outcome measure data will be entered into separate spreadsheets by two individual investigators.

**Data Editing** – Data means and standard deviations will be calculated each month and crossed- referenced between databases for each investigator. If means are different investigators will look to determine which outcomes differ. In the case that investigators cannot come to a consensus on the correct outcome measure, [name] will act as an arbiter.

**Updating** – Data may need to be updated due to an error in data entry. After the incorrect data point has been determined the investigator in charge of that data set should be notified and the Signature Log should be signed indicating who changed data in the spread sheet, what data was changed, for what reason was it changed as well as the time and date it was changed. A new database with the current date should be created. The previous database with the error should not be deleted.

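### Section 3.m allows a patient to be removed from the data set after a deviation, without requiring a decision blind to group or confining removal to a sensitivity analysis

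*Combined protocol and SAP*

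**What the plan says.** The rule is in the Procedures part of section 3.m: "Actions may be taken to remove a patient from the data set if the deviation affects the data collected". It is written in the passive, so the lack of a decision-maker does not come from the removal of names.

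The Definitions part of 3.m gives two terms. A deviation is a departure from the protocol "that is under the investigator's control and that has not been approved by the IRB". A violation is a deviation that may touch a participant's rights, safety or wellbeing, or the completeness, accuracy and reliability of the data. Procedures then gives two examples of potential violations: consent was not obtained, or "a patient is randomized that does not fit inclusion/ exclusion criteria". The removal sentence uses the wider term, deviation.

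On traceability, 3.m requires deviations to be logged and reported to the IRB, and 3.m.1 adds biannual reports to the safety officer and NIAMS. For correcting one data value, section 3.O asks for a signed entry "indicating who changed data in the spread sheet, what data was changed, for what reason was it changed", with time and date, and the old database is kept. The staff roster in 3.c has a blinded investigator consulted on errors.

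The statistical text supplied (end of 3.O) covers only the transfer of data from Epi Info to SPSS. Section 3.a refers to Appendix A for the protocol.

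**The concern.** Randomisation protects a comparison only while the patients analysed are those who were randomised. The compliance checks in 3.m are made on the files of patients already assigned to a group, so the removal rule operates after randomisation. It takes out the whole patient, not the affected measurement, and nothing in it confines the removal to a secondary analysis.

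If the patients removed differ by arm and also differ in outcome, the group difference is biased and the type I error is no longer the nominal one. If removals are unrelated to outcome, only a little precision is lost. The wording does not ensure the harmless case. The manual also asks for more formality when one number is corrected than when a patient is dropped.

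**Working it through.** **Text check.** Four features would make the rule safe. The supplied text was read for each.

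- *Criterion linked to removal:* partly present. The violation definition is close in substance to the removal condition, and there are two examples, but no sentence connects them to removal.
- *Decision blind to group:* not required. Section 3.h keeps blinded staff blind until outcomes for all patients are in the databases, but does not say who decides removals.
- *Removal limited to a sensitivity analysis:* not stated.
- *As-randomised analysis set:* not in any supplied section; Appendix A is unseen.

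**Size.** The plan has no figure of its own to reproduce here. It gives a goal of 90 patients (3.e.1) and three groups (3.g), so 90 / 3 = 30 per arm if allocation is equal, which is an assumption. The expected number of removals, the test and the significance level are not in the supplied text. Assumed: one to three removals, a normal outcome with SD 1, no true effect, and a two-sided 5% t-test of two arms.

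Removing k patients who lie on average m SD below their arm's mean raises that mean by k × m / (30 − k).

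- *Drawn at random from the worse half of one arm:* m is about 0.78 (simulated mean of the lower 15 of 30 normal values).
  - k = 1: 0.78 / 29 = 0.027 SD
  - k = 2: 1.56 / 28 = 0.056 SD
  - k = 3: 2.34 / 27 = 0.087 SD
- *Worst three of one arm:* m is about 1.67, so 3 × 1.67 / 27 = 0.19 SD.

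Simulated type I error (500,000 to 1,000,000 trials per case):

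| Removal | Shift (SD) | Type I error |
|---|---|---|
| Three at random | 0.00 | 5.0% |
| Worse half of one arm, k = 1 / 2 / 3 | 0.03 / 0.06 / 0.09 | 5.0% / 5.3% / 5.9% |
| By a score correlated 0.5 with outcome, one arm, k = 1 / 2 / 3 | 0.04 / 0.07 / 0.09 | 5.3% / 5.9% / 6.7% |
| Worse half, three from one arm and one from the other | 0.06 | 5.2% |
| Worst three of one arm (bound) | 0.19 | 12.6% |

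A separate run with 40,000 trials gave 12.3% for the last row.

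**Price of keeping everyone.** With 30 per arm, an effect of 0.736 SD has 80% power. If k active-arm patients gain nothing and stay in, the mean effect becomes 0.736 × (30 − k) / 30, that is 0.711, 0.687 or 0.662 SD for k = 1, 2 or 3. Simulated power is 76.9%, 73.8% or 70.5%. If the same patients were removed without bias, power would be 79.3%, 78.6% or 77.8%.

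**The case against.** The strongest reply is that this is an operating manual. An analysis population belongs in the protocol, and that is Appendix A. If Appendix A has the rule, what remains is a conflict of wording. This stands and limits the strength of the point. Even so, the removal sentence is a live instruction to staff and would still need to be reconciled.

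Second, a criterion does exist in outline, and one example is a proper ground for removal: a patient who never consented should not have data in the study. Both stand. A reader might infer that the rule has no criterion at all; the definitions do not support that. What is missing is the link.

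Third, deviations are logged and reported as they occur, so the pool of removable patients is largely on record before groups are compared. This limits selection after the fact, but it does not settle who is analysed.

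Two stronger readings are tempting.

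- *The decision would be made by people who know the arm.* The principal investigator receives the compliance reports and takes part in checking that assignments "for each of the first 10 participants that are randomized from each list match the assignment from the envelopes". The person monitoring compliance cross-references the lists. One person on the unblinded list is "in charge of initial randomization and study analysis". Yet no section gives any of them the removal decision. Watching sessions separates TE only from the device arms, but the sham display is identical to the active one.
- *Device errors would make removals unequal by arm.* Only two arms receive a unit, and the sham unit is "specifically configured to cease TENS current output 20 seconds after the participants initiation". But device set-up is not among the checks listed in 3.m, and no section describes such an error or expects removals. Low use by patients is largely outside the definition of a deviation, which concerns the investigator's control.

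**Conclusion.** The point holds as a gap in a stated exclusion rule. The supplied text permits removal of a randomised patient from the data set without a blind decision and without confining it to a sensitivity analysis, and it shows no as-randomised set. It does not show that removals would be unblinded, unequal by arm or numerous.

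The worse-half and correlated-score cases stay at or below 0.09 SD and 6.7% type I error, even with one to three removals all from one arm. The figure of 12% to 13% needs deliberate deletion of the three worst outcomes in one arm and should not be read as a forecast. All sizes rest on the assumed 30 per arm, normal outcome, t-test and number of removals. The point is conditional on Appendix A. Rating: minor, a cheap improvement.

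**What to change.** Replace the removal sentence in 3.m with:

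> All randomised, consented participants are analysed in the group to which they were randomised, whatever their deviations. A measurement shown in the source record to be technically invalid is set to missing for that visit only, by staff blind to group, with the reason logged before any comparison by group. Any exclusion of patients, including those randomised in error, is confined to a sensitivity analysis whose membership is fixed by staff blind to group before any comparison by group, and is reported by arm with reasons.

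If Appendix A already defines the analysis set, reconcile 3.m with it.

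The change is one of wording and uses blinded staff the trial already has (3.c, 3.h). Its price is that off-protocol data stay in the primary analysis. In the example above with three non-benefiting patients, power is about 70% instead of 78%, and the sensitivity analysis would make that difference visible. Some judgement remains over what counts as technically invalid, and the handling of the resulting missing values should be stated in the same place.
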